7.3. Lost to Follow up

A participant will be considered lost to follow-up if he or she repeatedly fails to return for scheduled visits and is unable to be contacted by the study site. Site personnel are expected to make diligent attempts to contact participants who fail to return for a scheduled visit or were otherwise unable to be followed up by the site.

Site personnel, or an independent third party, will attempt to collect the vital status of the participant within legal and ethical boundaries for all participants randomized, including those who did not get investigational product. Public sources may be searched for vital status information, subject to local regulations. If vital status is determined, this will be documented and the participant will not be considered lost to follow-up.

Lilly personnel will not be involved in any attempts to collect vital status information.

Discontinuation of specific sites or of the study as a whole are handled as part of Section [10.1.8](#).

8. Study Assessments and Procedures

Unless otherwise stated in the subsections below, all samples collected for specified laboratory tests will be destroyed within 60 days of receipt of confirmed test results. Certain samples may be retained for a longer period, if necessary, to comply with applicable laws, regulations, or laboratory certification standards.

- Study procedures and their timing are summarized in the SoA. Protocol waivers or exemptions are not allowed.
- Immediate safety concerns should be discussed with the sponsor immediately upon occurrence or awareness to determine if the participant should continue or discontinue study intervention.
- Adherence to the study design requirements, including those specified in the SoA, is essential and required for study conduct.
- All screening evaluations must be completed and reviewed by the investigator to confirm that potential participants meet all eligibility criteria. The investigator will maintain a screening log to record details of all participants screened and to confirm eligibility or record reasons for screening failure, as applicable.
- Procedures conducted as part of the participant's routine clinical management (e.g., blood count) and obtained before signing of the ICF may be utilized for screening or baseline purposes provided the procedures met the protocol-specified criteria and were performed within the time frame defined in the SoA.
- Additional safety assessments (for example, ECG and labs) may be performed at investigator's discretion.

8.1. Efficacy Assessments

8.1.1. Imaging

Efficacy assessments include tumor evaluation every 8 weeks after treatment initiation through week 24, and then every 12 weeks thereafter as noted in the SoA. Images are to be submitted for BICR evaluation within 5 days of completion. Patients who discontinue treatment without radiographic progression by BICR should continue to be assessed per the above schedule until radiographic disease progression is confirmed by BICR or death.

All patients are required to undergo neck, chest, abdomen, and pelvis imaging at baseline and subsequent serial imaging at disease assessment time points. All images will be collected at a central facility for central reviewer assessment during the study. Response will be assessed per RECIST 1.1 requirements (Eisenhauer et al., 2009).

Finally, all patients will enter Long-Term Follow-Up (LTFU) for confirming disease progression (if not occurring on treatment), subsequent anticancer therapy(ies), and survival.

Baseline disease assessment with radiographic tumor measurements using computed tomography (CT) or magnetic resonance imaging (MRI) of neck, chest, abdomen, and pelvis or any other areas with suspected disease involvement must be completed within 28 days of C1D1. MRI with contrast is the preferred imaging modality for imaging the abdomen and pelvis of subjects with

MTC given the inherent challenges in RECIST 1.1 assessment of MTC liver metastases. If MRI is not obtainable, triple phase CT of the abdomen (nonenhanced, arterial phase, and portal venous phase imaging) with pelvis is recommended. Routine single-phase CT of the abdomen and pelvis in the portal venous phase if the recommendations listed above are not obtainable. Brain imaging is required at baseline only for patients with a history of CNS metastases, or if clinically indicated and subsequent serial scans are required if brain metastases are present at baseline (MRI preferred, CT with contrast is acceptable if MRI contraindicated). Bone imaging is required at baseline only for patients with known bone metastases or if clinically indicated, and subsequent serial scans are required if bone metastases are present at baseline (MRI or CT with bone windows preferred).

For each modality, IV and oral contrast should be utilized (chest CT does not require contrast) unless there is a clear contraindication (e.g., decreased renal function or allergy that cannot be addressed with standard prophylactic treatments). Post-baseline imaging should be performed every 8 weeks (± 7 days) for 24 weeks and every 12 weeks (± 7 days) thereafter, including imaging of the neck, chest, abdomen, and pelvis, and any other known sites of disease, using the same modality(ies) as used for baseline imaging obtained during the screening period until PD, withdrawal of consent, or death. For the purpose of determining progression for eligibility, a change in modality *may* be acceptable if clear progression can be confirmed by central review, especially when a less sensitive modality was used for the second scan (e.g., liver metastases present on CT abdomen occurring after a previously normal MRI abdomen). Additional studies can also be performed at any time as clinically indicated. Please see the Site Imaging Manual for guidelines on how the various imaging studies should be performed and transmitted for central review.

For patients who progress on study treatment and begin a different anti-cancer therapy (including patients who are initially assigned to the control arm and crossover to receive seliperatinib), PFS2 will be collected. It is recommended to maintain the study imaging schedule in patients who have discontinued treatment; that is, to continue imaging every 8 weeks for the first 24 weeks of the next therapy, then every 12 weeks, as much as allowed according to the patient's new treatment standard of care. These images will be collected centrally and the overall tumor assessment should be entered into the CRF.

8.1.2. BICR Assessment

Response assessments, including verification of PR or CR and disease progression will be assessed by BICR. These data will constitute the primary assessment for PFS and best overall response (BOR) analyses. The BICR will conduct assessment of tumor response by RECIST 1.1.

Following each scan, the investigator will assess for progression using RECIST 1.1 and submit the scan for BICR review as outlined in Section 1.3. The table below outlines the potential actions following BICR review of imaging.

| Investigator assessment | BICR assessment | Actions |
|----------------------------------|--|--|
| Progressive Disease ^a | Progression verified | 
 • Discontinue study treatment OR • Continue study treatment with sponsor approval if the patient is believed to be clinically benefitting OR • Crossover to selpercatinib (only patients progressing on Arm B are eligible for crossover) |
| | Progression not verified | 
 • Continue on study treatment if the patient is believed to be clinically benefitting until a criterion for discontinuation is met OR • Discontinue study treatment; imaging and submission for central review should continue until 
 1. radiographic disease is verified by the BICR, 2. death, 3. withdrawal of consent, or 4. study completion. 
Patients on Arm B would be eligible to cross over upon BICR documentation of progression.
 |
| Non-progression | In the case of investigator-assessed non-progression, results are not reported back to investigator as BICR assessment is only used for endpoint assessment. | 
 • Continue on study treatment until progressive disease or another criterion for discontinuation is met |

^a For patients where the investigator assessment is PD, it is at the discretion of the investigator if study treatment is continued until the BICR assessment is received.

In the crossover period scans will be collected and stored for future review, if needed.

8.2. Safety Assessments

For each patient, AEs, ECGs, vital signs, laboratory tests, and other tests should be collected as shown in the SoA (Section 1.3).

Results from any clinical laboratory test analyzed by a central laboratory (refer to Section 10.2) will be provided to investigative sites by Lilly or its designee.

Refer to Section 8.3 for details on the recording of AEs.

Lilly will periodically review evolving aggregate safety data within the study by appropriate methods.

Planned time points for all safety assessments are provided in the SoA.

Tanner staging (Marshall and Tanner 1969, Marshall and Tanner 1970) is required for any patient under age 18 (until sexual maturity is reached) in order to monitor the development of adolescent patients treated with selpercatinib.

Participants who have not yet obtained full adult height will undergo MRI of one knee at baseline and every 6 months while the growth plate remains patent. Right knee is preferred, but whichever knee is imaged at baseline should be imaged at all time points.

Adolescents who have had a documented growth rate of <1 cm/year over the prior 2 years and/or have reached a midparental height of over 152 cm in girls and 167 cm in boys, are likely to have obtained full adult height. If it is unclear that a patient has obtained full adult height, pretreatment tibial radiographs (AP and lateral views) of the right knee should be obtained and MRI performed only if the growth plate remains patent. If the growth plate remains patent, the patient will have a MRI performed every 6 months until the growth plate is no longer patent.

In addition, a Safety Follow-up (SFU) visit 28 days (± 7 days) after the last dose of selpercatinib, cabozantinib, or vandetanib will occur to determine the status of unresolved AEs.

8.2.1. Electrocardiograms

- ECG monitoring should be performed as outlined in the SoA (Section 1.3). QTcF values should be recorded on the CRF. In addition, Lilly may request a copy of the ECGs for adjudication.

The actions below should be taken if the QTcF is greater than 500 msec on at least 2 of 3 ECGs (i.e., Grade 3 prolongation per CTCAE) and the triplicate average QTcF is greater than 500 msec OR is >60 msec longer than baseline QTcF:

- Manually review to confirm accuracy. ECGs will be interpreted by a qualified physician (the investigator or qualified designee) at the site for immediate patient management.
- Assess for alternative causes (concomitant medications, electrolyte abnormalities, presence of pacemaker). Clinical chemistry should be assessed and if electrolytes are abnormal, they should be repleted as indicated. Potassium should be ≥ 4 meq/L and less than the upper limit of normal (ULN) and magnesium and calcium should be within normal limits. Dose adjustment is not required if an alternative cause is found and if, in the medical judgment of the investigator, the patient is able to safely continue study treatment at his/her current dose while the cause of QTc change is being addressed.
- Institutional guidelines or standard of care measures for management of QTcF interval >500 msec and/or associated arrhythmias should be initiated.
- If the patient is on Arm A, selpercatinib should be reduced at least 1 dose level.
- If the patient is on Arm B1 (cabozantinib), dose adjustments should occur per label/institutional guidelines.
- If the patient is on Arm B2 (vandetanib), treatment should be held until QTcF returns to <450 msec, then reduce vandetanib by 1 dose level. If a further event of CTCAE Grade 3 or higher toxicity or prolongation of the ECG QTc interval occurs, dosing with vandetanib should be permanently stopped. The patient must be monitored appropriately.

Fridericia's QT Correction Formula

| Formula | Fridericia $QTcF = QT / (RR)^{1/3}$ |
|---------|--|
|---------|--|

Abbreviations: QT = ECG interval measured from the onset of the QRS complex to the offset of the T wave; QTcF = QT interval corrected for heart rate using Fridericia's formula; RR = time between corresponding points on 2 consecutive R waves on ECG.

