6.6. Dose Modification

Intolerable AEs that lead to treatment discontinuation (except alopecia) will meet criteria to be included in the TFFS endpoint. Intolerable AEs are defined as any study drug-related AE that meets protocol guidance for treatment discontinuation.

- Permanently discontinue treatment for any of:
 - Cabozantinib: development of visceral perforation or fistula formation, severe hemorrhage, serious arterial thromboembolic event (e.g., myocardial infarction, cerebral infarction), nephrotic syndrome, malignant hypertension, hypertensive crisis, persistent uncontrolled hypertension despite optimal medical management, osteonecrosis of the jaw, reversible posterior leukoencephalopathy syndrome
 - Vandetanib: development of prolonged QT interval not improved with electrolyte correction and/or dose reduction, severe skin reactions, ILD, ischemic cerebrovascular events, hemorrhage, heart failure, persistent uncontrolled hypertension despite optimal medical management, or reversible posterior leukoencephalopathy syndrome
 - Selpercatinib: malignant hypertension, hypertensive crisis, persistent uncontrolled hypertension despite optimal medical management, or severe/life-threatening hemorrhage. Patients with clinical benefit who experience recurrent hypersensitivity reaction or recurrent AST or ALT increase despite dose reductions should be

discussed with the Lilly medical team and may be allowed to continue treatment with more than 2 dose reductions if continuation is considered to be safe and in their best interest

Dose reductions should be made according to the following parameters using the dose reduction table below. Interrupt dosing for CTCAE v5.0 Grade 3 or greater AEs or Grade 2 AEs not resolved within 48 hours with appropriate supportive care (e.g., nausea not improved with antiemetics) and considered intolerable by the patient or the investigator.

- For selpercatinib related hypersensitivity, liver function test abnormalities, thrombocytopenia, and hypertension, see dose adjustments below in Sections 6.6.1, 6.6.2, 6.6.3, and 6.6.4, respectively.
- Regardless of treatment arm, study treatment may continue for hypertension that is considered Grade 3 on the basis of requiring ≥ 2 anti-hypertensives or more intensive anti-hypertensive therapy than baseline once blood pressure is stabilized.

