- Dose modifications for ECG changes are described in Section 8.2.1. If a patient receiving selpercatinib or cabozantinib experiences QTcF > 500 msec despite 2 dose reductions and if the investigator deems it in the best interest of the patient, the patient may continue treatment with study drug with Lilly medical approval. In addition, Lilly will request a copy of the ECGs for adjudication.
- Upon resolution (or return to patient's baseline) of AEs at least possibly related to treatment, reduce the dose as follows:
 - If previously receiving dose level 1, resume treatment at dose level -1
 - If previous receiving dose level -1, resume treatment at dose level -2
 - If previously receiving dose level -2, resume treatment at the same dose level. If a second AE requiring dose modification occurs at dose level -2, discontinue study treatment.
 - For AEs clearly unrelated to study treatment that resolve or return to patient's baseline in ≤ 14 days, dose reduction is not required.
 - Re-escalation to a prior dose level after a dose reduction is permitted once the AE requiring dose reduction is resolved. See Sections 6.6.1 through 6.6.4 and the IB for specific dose adjustments required for patients receiving selpercatinib.
 - Above are guidelines and may be superseded by local practice guidelines or advice per the local cabozantinib/vandetanib labels when appropriate.

Except as noted, a maximum of 2 dose level reductions will be allowed. Any patient requiring > 42 days omission of treatment for drug-related toxicities will meet the criteria for study treatment discontinuation. Treatment omissions of > 42 days in extenuating circumstances that are not drug-related (e.g. recovery from motor vehicle accident) may be approved by the Lilly medical team.

General Dose Reductions for Treatment Related Toxicities^a

| Dose Level | Time | Selpercatinib Dose (mg) | Cabozantinib Dose (mg) ^b | Vandetanib Dose (mg) |
|---------------|------|-------------------------|-------------------------------------|----------------------|
| Dose Level 1 | AM | 160 | 140 | 300 |
| | PM | 160 | - | - |
| Dose Level -1 | AM | 120 | 100 | 200 |
| | PM | 120 | - | - |
| Dose Level -2 | AM | 80 | 60 | 100 |
| | PM | 80 | - | - |

^a Unless other specific dose reductions, as per Sections 6.6.1, 6.6.2, 6.6.3, and 6.6.4.

In the instance that vandetanib 100-mg tablets are unavailable, but vandetanib 300-mg tablets are available, the below table is to be followed in adult patients.

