Vandetanib Dose Modification using 300-mg Tablets for Adult Patients

| Dose Level of Vandetanib | Vandetanib 300-mg tablets ^a |
|----------------------------|--|
| Dose Level 1 | 1 tablet QD every day |
| Dose Level -1 ^b | 1 tablet QD for 2 days, every 3 days |
| Dose Level -2 ^b | 1 tablet QD for 1 day, every 3 days |

Abbreviations: QD = once daily.

^a A starting dose of vandetanib should be 200 mg in adult patients with moderate renal impairment (creatinine clearance results between 30 and 50 mL/min).

^b These dose regimens are expected to give similar reduced exposure corresponding to dose levels -1 and -2 in the standard dose modification table (General Dose Reductions for Treatment Related Toxicities).

Selpercatinib General Dose Reductions for Treatment Related Toxicities for Adolescent Patients

The dose (regardless of BSA calculation) should be no higher than the corresponding adult level for dose adjustments (e.g. Dose Level -1, 120 mg and Dose Level -2, 80 mg). Please see the table in Section 6.1.2 for selpercatinib dose rounding.

| Dose Level | Time | Selpercatinib Dose (mg/m ²) |
|---------------|------|---|
| Dose Level 1 | AM | 92 |
| | PM | 92 |
| Dose Level -1 | AM | 70 |
| | PM | 70 |
| Dose Level -2 | AM | 46 |
| | PM | 46 |

Vandetanib General Dose Reductions for Treatment Related Toxicities and Starting Dose for Moderate Renal Impairment for Adolescent Participants

| BSA (m ²) | Dose Reduction (mg) ^a or Starting Dose with Moderate Renal Impairment |
|-----------------------|--|
| 0.7 - <0.9 | - |
| 0.9 - <1.2 | 100 QOD |
| 1.2 - <1.6 | 100 QD |
| ≥1.6 | 7 day schedule: 100-200-100-200-100-200-100 |

Abbreviations: BSA = body surface area; QD = once daily; QOD = once every other day.

- a Participants with an adverse reaction requiring a dose reduction should stop taking vandetanib for at least a week. Dosing can be resumed at a reduced dose thereafter upon resolution or return to patient's baseline.

See Section 8.2.1 for additional information on dose reduction related to prolonged QTc.

Cabozantinib General Dose Reductions for Treatment Related Toxicities for Adolescent Participants

| BSA (m ²) | Weekly Dose/Schedule for 1 st Dose Reduction due to Toxicity | Weekly Dose/Schedule for 2 nd Dose Reduction due to Toxicity |
|-----------------------|---|---|
| 0.35 – 0.39 | 60 mg = 20 mg M, W, F | Off therapy |
| 0.40 – 0.45 | 80 mg = 20 mg M, W, F, Sun | 60 mg = 20 mg M, W, F |

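### For an adult on vandetanib already reduced for QTc, Protocol 8.2.1 and 6.6 give opposite instructions after a later non-ECG Grade 3 or higher toxicity, and whether the stop counts for TFFS depends on which section is applied

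*Protocol*

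**What the plan says.** **Protocol 8.2.1 (Electrocardiograms).** For a vandetanib patient who meets the QTcF trigger at the head of the list, "treatment should be held until QTcF returns to <450 msec, then reduce vandetanib by 1 dose level". If, after that, a "further event of CTCAE Grade 3 or higher toxicity or prolongation of the ECG QTc interval occurs, dosing with vandetanib should be permanently stopped".

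**Protocol 6.6 (Dose Modification).** The general ladder applies to all three drugs once a treatment-related AE has resolved: "If previous receiving dose level -1, resume treatment at dose level -2". It adds: "Except as noted, a maximum of 2 dose level reductions will be allowed". Two sentences point elsewhere for QT matters: "Dose modifications for ECG changes are described in Section 8.2.1" and, under the adolescent vandetanib table, "See Section 8.2.1 for additional information on dose reduction related to prolonged QTc". The vandetanib list of reasons for permanent discontinuation includes "development of prolonged QT interval not improved with electrolyte correction and/or dose reduction"; it has no item for a Grade 3 toxicity that follows an earlier QTc event. The footnote to the dose-reduction table names 6.6.1 to 6.6.4 as exceptions and does not name 8.2.1. Section 6.6 also describes its rules as guidelines that local practice or the local label may override.

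**TFFS.** Protocol 6.6 and 9.4.3.2.1 and SAP 8.4.1.1.2 count a drug-related AE leading to discontinuation only if it satisfies the protocol's own rules for stopping. An independent committee decides this retrospectively on blinded data. Protocol 8.3 says discontinuation for an AE should follow the criteria in 6.6.

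**The concern.** A site that follows 8.2.1 to the letter and a site that follows 6.6 to the letter can treat the same patient in opposite ways, and each can claim compliance. That is a conduct problem in itself.

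It also reaches an endpoint. TFFS is a type I error-controlled key secondary endpoint and the gatekeeper to comparative tolerability, whose denominator is time on treatment. If the stopping rule for part of the control arm differs between two sections, the committee has no single standard against which to judge a stop. Blinded review does not settle which section is the standard.

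**Working it through.** **1. The case where the sections conflict.** Take an adult on vandetanib 300 mg with a qualifying QTc event that recovers.

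- Both sections lead to a restart at level -1 (200 mg).
- The patient later has a drug-related Grade 3 event unrelated to the ECG, for example diarrhea.
- Section 6.6: interrupt and, on resolution, resume at level -2 (100 mg). The event is not on the vandetanib permanent-stop list.
- Section 8.2.1: stop permanently. Its sentence joins toxicity and QTc prolongation with an *or*, so the toxicity limb stands alone.
- Tie-breakers: the 6.6 pointer covers ECG changes, which this is not; the table footnote omits 8.2.1; Section 8.3 points to 6.6, where the 8.2.1 stop does not appear. No clause resolves the conflict.

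The adolescent vandetanib table has a single reduction step, so the ladder conflict concerns adults.

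**2. The case where they do not conflict on dose.** Suppose the later event is further QTc prolongation.

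- Section 6.6 twice hands QT-related dosing to 8.2.1 and qualifies its cap on reductions.
- Its allowance for continuing after two reductions opens "If a patient receiving selpercatinib or cabozantinib experiences QTcF > 500 msec despite 2 dose reductions", which leaves vandetanib out.
- So 8.2.1 governs, and 6.6 offers no competing second reduction.
- What remains is wording. The 6.6 stop item requires failure to improve; 8.2.1 requires further prolongation and does not say whether its opening threshold applies again.

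**3. The plan's own figures.** Inputs are 74 PFS events, HR 0.5, one-sided 2.5% and 2:1 allocation (Protocol 9.2), and Arm B medians of 25 months for PFS and 20 months for TFFS (Protocol 9.2; SAP Table JZJB.6).

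- Power: Φ(√(74 × 1/3 × 2/3) × ln 2 − 1.96) = Φ(4.055 × 0.693 − 1.96) = 80.3%. The plan states about 80%.
- TFFS count, with 250 patients (166.7 and 83.3), exponential times and common follow-up t: 166.7(1 − 2^(−t/50)) + 83.3(1 − 2^(−t/25)) = 74 gives t = 19.4 months.
- At that t, TFFS events are 166.7(1 − 2^(−19.4/40)) + 83.3(1 − 2^(−19.4/20)) = 47.6 + 40.8 = 88.4. With uniform accrual over 12 to 48 months (assumed) the count is 88.3 to 86.9. The plan states 88.

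**4. How large the affected component could be.**

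- Share of the Arm B TFFS hazard due to toxicity: 1 − 20/25 = 20%. Arm B failures with toxicity first: 0.20 × 40.8 ≈ 8, for both control drugs and all toxicities.
- The net excess of Arm B TFFS over PFS events is smaller, 40.8 − 34.7 = 6.1 (5.1 to 6.1 over the accrual range), because some of those patients would also have progressed by then.
- The documents give neither the vandetanib share nor a QTc rate. If 30 to 50% of 83 control patients receive vandetanib (25 to 42) and 5 to 15% of those have a first qualifying QTc event, 1.2 to 6.2 patients come under both sections. All four percentages are assumptions.
- Discordance also needs a later non-ECG Grade 3 or higher drug-related event, a stop made on the strength of 8.2.1, and no other reason to stop. No document supplies those rates, so the count is below 1 to 6 on these assumptions and otherwise unknown.

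**The case against.** The best defense is context. Section 8.2.1 is about ECGs, its opening trigger equates Grade 3 with QTc prolongation, and the history of amendment (d) describes the vandetanib sentence as QTc toxicity text moved there to keep ECG adjustments together. On that view the sentence was never meant to reach diarrhea, and a further event means one that meets the opening trigger again.

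That is a plausible account of intent, and it carries real weight for recurrent QTc. It does not remove the conflict. The operative sentence names toxicity and prolongation as alternatives, and reading the first as QTc only makes it largely a repeat of the second. A site acts on the sentence, not on the amendment history.

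Three further objections stand:

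- A TFFS event requires an actual discontinuation, drug-relatedness and central blinded adjudication, so events are not fixed by whichever section a site happened to read.
- Different QT rules for different drugs are not in themselves a defect. SAP sensitivity analysis SA1 for TFFS already tests continued selpercatinib after more than two reductions. It does not address the vandetanib stop.
- Section 6.6 calls its rules guidelines that a label may override. This explains some flexibility but adds another possible rule rather than choosing between the two.

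**Conclusion.** The contradiction holds for one defined patient: an adult on vandetanib, already reduced once for QTc, with a later non-ECG Grade 3 or higher drug-related AE. For recurrent QTc prolongation only a mismatch in stop wording remains.

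A reader might infer two stronger things. One is that 6.6 offers a rival second reduction after recurrent QTc prolongation; its cross-references to 8.2.1 rule that out. The other is that the conflict favors selpercatinib on TFFS. The documents do not support a direction: counting 8.2.1-only stops adds Arm B events, but a committee that applies 6.6, as Section 8.3 suggests, could decline to count them, and sites that follow 6.6 would not stop at all.

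The number of patients and the TFFS effect cannot be computed and are probably small. The 1-to-6 range above counts patients exposed to both sections under assumed rates, not discordant events, and should not be set against the roughly 8 toxicity failures as if it were. Primary PFS is unaffected by the classification, because it does not count toxicity and follows patients regardless of discontinuation. The point merits correction because the stopping instruction contradicts itself and feeds an error-controlled endpoint.

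**What to change.** Reconcile 8.2.1 with 6.6 so that:

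1. one rule, stated identically in both sections, covers a non-ECG Grade 3 or higher event in a vandetanib patient already reduced for QTc;
2. one definition of further QTc prolongation applies in 8.2.1 and in the 6.6 permanent-stop list.

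Which rule and which definition are for the sponsor's medical team. Depending on that decision, either add 8.2.1 to the exceptions listed in 6.6 or limit the scope of the 8.2.1 sentence. State in the TFFS committee's instructions which text is the protocol standard for discontinuation.

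For patients already treated, list any vandetanib discontinuations that satisfied 8.2.1 but not 6.6, and run one TFFS sensitivity analysis with their event status reversed.

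The cost is wording in two protocol sections, an instruction to the committee and one additional analysis run. No visits or tests are added.
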